 - f. Hospital admissions in the last 12 months (DKA, Hyperglycaemia, Hypoglycaemia, Non diabetes related)
 - g. Total daily dose of insulin (mean of previous 7 days)
 - h. Co-morbidities and medications
5. Psychology measures: Psychological scales will be administered to the parents on an electronic platform . (Questionnaires are included in the appendix)
 - a. Functional health status: Quality of life (QOL) WHO 5(11), EQ5D(12)
 - b. Fear of hypoglycaemia: Hypoglycaemia fear survey Parent(13)
 - c. Diabetes-related distress: Problem Areas in Diabetes PAID-Parent version(14)
 - d. Anxiety: GAD-7(15)
 - e. Sleep quality: Pittsburgh Sleep Quality Index(16)
 - f. Technology acceptance and satisfaction: DTQ(17)
6. Review pump settings and download capability.
7. Insertion of the first blinded sensor (next generation sensor and transmitter) to collect baseline glycaemic data. This constitutes first of the two sensors, each sensor provides data for 7 days. Parents will be instructed to test their children for a minimum 3 to 4x/day using the study meter provided. At this visit, all participants will be provided with the study meter and a participant record book.

VISIT 2

VISIT 2A (7 days after Visit 1)

Insertion of 2nd blinded sensor: Participants will return 7 days after sensor insertion to remove and download the first week of CGM data. The glucometer will be uploaded. A new sensor will be inserted and a fresh transmitter attached.

A total of 2 weeks of blinded sensor is required with at least 10 days of data (18). In participants who do not meet this requirement or if the sensor falls off/removed accidentally, repeat sensors will be offered till a maximum of 4 attempts of data collection (2B, 2C).

Hence, the run-in period duration will be over 2 to 4 weeks.

Visit 2B

1. The blinded sensor is removed
2. Insertion of 3rd blinded sensor (if applicable) and to be removed a week later
3. 24-hour food recall interview (to capture baseline dietary pattern)

Visit 2C Insertion of 4th blinded sensor (if applicable) and to be removed a week later

Participants who do not meet the run-in requirements i.e demonstrate ability to use CGM (in sensor naïve individuals) and/or have insufficient data on blinded CGM will not proceed to randomisation and will be withdrawn from the study.

VISIT 3 (Randomisation)

This visit is the treatment allocation visit (see section 4.4 for details).

The following data will be collected prior to randomization:

1. Diabetes clinical

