 - a. HbA1c
 - b. Total daily dose of insulin (mean of previous 7 days)
 - c. Severe hypoglycaemia in the run-in period
 - d. Diabetic ketoacidosis in the run-in period
 - e. Hospital admissions in the run-in period
2. Review carbohydrate (CHO) counting and offer dietetic support if needed
3. Pump upload and review of settings
4. Review of hypoglycaemia/hyperglycaemia management.

The control group will continue on their insulin pump therapy with or without CGM. They will attend the 3-monthly regular clinic appointments.

The intervention group will use the study device with the compatible CGM. They will attend additional visits required for device training and to review the pump settings. They will continue to attend their 3-monthly clinic appointments.

If needed, Visit 3 and 4A can be combined for intervention group.

VISIT 4 (Only for participants randomised to AHCL arm)

The additional visits for the HCL group are for device training to support the use of HCL.

Visit 4A: Pump training (2 hours)

Parents will be trained on how to use the Medtronic 780G insulin pump. They will be provided with a compatible meter (which communicates with the pump) along with the glucose strips for the study.

Visit 4B: CGM training (2 hours)

They will be instructed on how to link CGM on the Medtronic 780G pump and issued with compatible next generation sensor and transmitter, as well as CGM user guide. Initial low and high alarms will be set at 4.0mmol/L and 15mmol/L respectively, although these can be changed according to individual preference. Sensor naïve individuals will have familiarisation phase of 7 to 10 days to get used to wearing a sensor.

Visit 4A and 4B could be combined for participants familiar with sensors.

Visit 4C: Commencement of AHCL (1-2 hours)

Once CGM data has been established for a minimum of 3 to 7 days, participant returns for face-to-face instruction on AHCL use and initiation of 'SmartGuard'. During this visit, the sensor will be replaced to demonstrate sensor warm up and AHCL initiation, and provide an opportunity for those unfamiliar with CGM use to practice a sensor change with supervision.

Participants will subsequently have weekly communication via phone call or email for support for the following 4 weeks, and upload their pump weekly. Investigators will log all time spent training and in communication with participant. Communication can be more often – as per clinical need, and logged.

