4.3 Bias

4.4 Blinding and Randomisation

To minimise bias, participants will be allocated to treatment group based on minimisation. Blinding is not possible in this open label study and hence the maintenance of breaking codes is not required.

Minimisation will be used to allocate participants to study group based on the following balancing factors measured at baseline: age at Visit 1 (<6 years, 6 years and above), time in target range (<55%, greater or equal to 55%) collected from blinded sensor data, and study site. Minimisation is a method of ensuring excellent balance between groups for known prognostic factors(20). The Minimpy program (MinimPy)(19) will be used to allocate participants. Allocation will be undertaken by the delegated persons at Perth Children's Hospital.

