4.9 Trial Termination

Study participation is voluntary, and participants may withdraw at any time. The DSMB will report to the ethics committees and investigators if stopping the study is required.

In general, once a participant is randomised, he/she will remain in the study unless the investigator believes it is not safe for the participant to continue. However, the criteria below will be used to determine whether use of the AHCL should be discontinued for a participant.

1. Severe hypoglycaemia (seizure or coma or any episodes requiring glucagon).
2. Severe diabetic ketoacidosis (venous ph <7.2)
3. Non-compliance with the protocol or development of a new medical condition or need for chronic use of a medication which in the judgment of the investigator increases risk for the participant

If AHCL use is stopped according to the above criteria, but the participant is willing, they will remain in the study and will continue to make all of the scheduled visits and participate in all monitoring.

The primary analysis will be intention to treat. Since participants in the usual care arm are following their normal diabetes care regimen, there will be no change in their participation in the study if they experience one of the events that would trigger stopping.

Criteria for Suspending/Stopping Overall Study

The DSMB will provide guidance to the Lead Investigator as to whether the overall study should be stopped.

In case of a recurring system malfunction or participant safety issue observed with multiple participants, the overall study will be suspended while the problem is diagnosed. The study may resume if the underlying problem can be corrected by a protocol or system modification that will not invalidate the results obtained prior to suspension.

The primary safety outcome will be

Severe hypoglycaemia (coma, convulsion or any episodes requiring glucagon). A sequential monitoring approach described by Kramar and Bascoul-Mollevi (2009) will be taken to determine study cessation rules due to excess severe hypoglycaemia. As hypoglycaemia events are experienced during the study, the DSMB will be notified in real time. The maximum acceptable rate of severe hypoglycaemia as well as the approach taken with regard to 'alpha spend' to preserve the nominal alpha of 0.05 will be determined in conjunction with the DSMB prior to the commencement of the study.

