An instance of severe DKA from Automode use (algorithm-related) in the AHCL group will result in temporarily stopping additional enrolment of participants until DSMB review of the data to determine whether the event was triggered by the system or not and whether it is safe to proceed. An emergency meeting of the DSMB will be convened within 7 days to review the data. In addition, the DSMB Chair may request a meeting at any time.

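### After one algorithm-related severe DKA, the only mandatory hold on trial activity is on further enrolment; SmartGuard starts in children already allocated to AHCL are left to discretion

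*Protocol*

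**What the plan says.** Protocol section 4.9, under the criteria for suspending or stopping the overall study, deals with a single algorithm-related severe DKA in the AHCL group. Such an event "will result in temporarily stopping additional enrolment of participants until DSMB review of the data", so that the DSMB can judge whether the system was the trigger and whether the trial may safely go on. The section continues: "An emergency meeting of the DSMB will be convened within 7 days to review the data". The DSMB Chair may also ask for a meeting at any time.

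Other provisions bear on the same event:

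- Section 8.2(h) requires a DKA admission to be reported to the principal investigator within 24 hours, with the lead site notified.
- Section 4.9 lists severe DKA among the criteria for deciding whether AHCL should be discontinued in the affected child.
- For the trial as a whole, section 4.9 says that in case of a "recurring system malfunction or participant safety issue observed with multiple participants, the overall study will be suspended".
- A randomised child otherwise stays in the study "unless the investigator believes it is not safe for the participant to continue".
- On stopping: "The DSMB will provide guidance to the Lead Investigator as to whether the overall study should be stopped".

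Section 4.2 fixes when exposure starts. Of the blinded-sensor phase it says: "Hence, the run-in period duration will be over 2 to 4 weeks". Allocation is at Visit 3. SmartGuard is switched on at Visit 4C: "Once CGM data has been established for a minimum of 3 to 7 days, participant returns for face-to-face instruction on AHCL use". Sensor-naive children also have a familiarisation phase of 7 to 10 days.

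**The concern.** The pause exists so that the DSMB can decide whether the algorithm caused a severe DKA before more children are put at risk. It is attached to enrolment, but a child meets the algorithm at Visit 4C, days to weeks further on. A child allocated to AHCL who has not yet reached Visit 4C falls outside the hold, and no other rule covers that child after a single event.

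What is at stake is narrow. A child in the trial's 2 to 7 age range could start an investigational algorithm during the days when its role in a severe DKA is under urgent review, and four sites could decide differently. Trial validity is not at stake.

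**Working it through.** The plan gives no figure on this point, so the first three steps set the rules side by side. The last two give a sense of scale.

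**1. What one event triggers, and what each rule holds**

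- Section 4.9, DKA paragraph: holds further enrolment and convenes the DSMB within 7 days.
- Section 8.2(h): a report within 24 hours; holds nothing.
- Section 4.9, discontinuation criteria: concern AHCL use in the affected child only.
- Section 4.9, overall suspension: needs a recurring malfunction or several participants, so one event does not meet it.
- Section 4.9, default for randomised children: they stay in, subject to the investigator's judgement case by case.

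None of these requires Visit 4C to be deferred for a child already allocated.

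**2. Shortest route to exposure (section 4.2)**

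- Visit 3 to Visit 4C: at least 3 days of CGM data, with Visits 3, 4A and 4B combined. No maximum is stated.
- Visit 1 to Visit 4C: 2 sensors × 7 days + 3 days = 17 days.

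**3. Two readings of enrolment, which is not defined**

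- *Visit 1.* A new enrolee is at least about 17 days from SmartGuard. Since 17 > 7, the pause prevents no start within 7 days.
- *Visit 3.* New allocations stop, so some starts may be prevented when the lag to Visit 4C is under 7 days. Children already allocated are still not covered.

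**4. How many children**

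Inputs: 70 participants in two equal groups (section 9.2) give 35 on AHCL. Assumptions: starts are spread evenly over 12 to 18 months, because no accrual curve is given, and a month is 30.44 days. All counts are conditional on the event, for which the protocol states no rate.

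- Start rate: 35/18 = 1.94 to 35/12 = 2.92 per month.
- Already-allocated children starting in a 7-day hold = rate × min(lag, 7)/30.44. Low: 1.94 × 3/30.44 = 0.19. High: 2.92 × 7/30.44 = 0.67.
- All starts in 7 days, run-in children included: 1.94 × 7/30.44 = 0.45 to 2.92 × 7/30.44 = 0.67.
- Over a wider assumed accrual of 9 to 21 months (52/12 weeks per month), all starts in 7 days are 35/91 = 0.4 to 35/39 = 0.9, still under one.
- Already on SmartGuard, if the outcome window opens at week 13 (91 days) and the lag is 3 to 10 days: 1.94 × 81/30.44 = 5.2 to 2.92 × 88/30.44 = 8.4.

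Seven days is the limit for convening the meeting, not a cap on the hold. In a hold of 17 days or more with an assumed 17-day lag (10 days of familiarisation, then 7 of CGM data), the count would be 1.94 × 17/30.44 = 1.1 to 2.92 × 17/30.44 = 1.6.

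**5. What a 7-day hold costs a held child**

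Share of SmartGuard time lost before the outcome window = 7/(window start − lag), for assumed lags of 3, 10 and 17 days:

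- Window at week 13 (section 7.1), 91 days: 7/88 = 8.0%, 7/81 = 8.6%, 7/74 = 9.5%.
- Window at week 11 (Visit 5, control arm), 77 days: 7/74 = 9.5%, 7/67 = 10.4%, 7/60 = 11.7%.

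One held child among 35 lowers the arm's mean SmartGuard time by at most 11.7%/35 = 0.3%.

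**The case against.** The strongest reply is that sections 4.9 and 8.2 form a coherent graded response: individual assessment of the affected child, an enrolment pause with urgent DSMB review after one algorithm-related event, and suspension if the problem recurs or spreads. Section 4.7 makes the investigators responsible for patient safety. SmartGuard starts only at a face-to-face staff visit, followed by weekly contact for four weeks. Allocation is central ("Allocation will be undertaken by the delegated persons at" the lead hospital), and the lead site would know of an admission quickly. The proposed change also leaves the 5 to 8 children already on SmartGuard to judgement; the starters it would hold number only about 3/88 = 3% to 7/81 = 9% of that group.

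Most of this stands, and it is why the point is minor. Staff could defer a start, and probably would. It does not remove the gap: the protocol chose to write a mandatory pause and attached it to a step that precedes exposure. Starting a child is also a different decision from withdrawing one who is established on the device, so discretion for the second group does not argue for silence on the first.

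A reader might infer that stopping enrolment is the only mandatory step after such an event. The documents do not support that: the DSMB meeting and the 24-hour report are also mandatory, and severe DKA is a discontinuation criterion for the affected child. Nor do they support the reading that starts must go ahead during the review. The protocol neither requires nor forbids them.

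**Conclusion.** The point holds as a minor clarification of a safety rule. On the text, enrolment is the only trial activity that must be held after one algorithm-related severe DKA, and on either reading of enrolment a child already allocated to AHCL is not covered. That conclusion needs no assumption.

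The size does. Under even accrual over 12 to 18 months, 0.2 to 0.7 already-allocated children would start SmartGuard in a 7-day hold. The figure depends on the assumed accrual and lag, could pass one child if the DSMB took well over a week to report, and applies only if a rare event occurs. A reader might infer a threat to the primary comparison; there is none of any consequence, since the few affected children would at most have their start shifted by days.

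**What to change.** Amend section 4.9 in substance as follows: *Until the DSMB has reported, new consent (Visit 1), randomisation (Visit 3) and SmartGuard initiation (Visit 4C) are all held. Children allocated to AHCL who have not started SmartGuard stay in Manual Mode or on their own pump. The DSMB decides whether children already using SmartGuard continue.*

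Naming the three visits also removes the ambiguity over what enrolment means.

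The cost is two or three sentences and, after a rare event, about a week's wait for a child or two. Children in run-in would have slightly older baseline CGM data at randomisation. An allocated child who is held loses about 8 to 12% of SmartGuard time, because the outcome window is timed from randomisation. The fallback is already in place: the study pump has a Manual Mode (section 4.1), and section 8.2 already provides for a return to the child's own pump.

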4.10 Data identification

Every participant will be given a unique study number. All data on CRF will be de-identified.

5 Source and Selection of Participants

5.1 Source of Participants

Eligible participants will be identified through the Western Australian Children's Diabetes Database (WACDD) and state specific databases. A generic invite with the information sheet will be sent electronically. Participants will also be identified during their clinic visits. We may also use advertisements, notices, and/or media to recruit participants. Examples include flyers posted in public settings, newspaper ads, and radio and television advertisement. All advertisements and recruitment materials (e.g., video, audio, and telephone scripts) will be submitted to HREC for prior approval.

The inclusion and exclusion criteria are the same for both phases. Participants in the feasibility phase are permitted to participate in the RCT after a minimum wash-out period of 3 months.

5.2 Participant inclusion criteria.

1. Type 1 diabetes (diagnosis consistent with American Diabetes Association Classification of Diabetes Mellitus, diagnosed at least 1 year ago)
2. CSII therapy for at least 3 months
3. Age 2 to ≤ 7 years
4. HbA1c $\leq 8.5\%$ in the last 3 months
5. Total daily insulin of ≥ 8 units/day for the last two weeks
6. Participant and parent willing to follow study instructions
7. Living in an area with internet and cellular coverage

5.3 Participant exclusion criteria.

1. Commenced CGM in the 3 months prior to screening visit
2. Using advanced hybrid closed loop system: Control IQ
3. Uncontrolled coeliac disease
4. Uncontrolled thyroid disease
5. Inability or unwillingness to meet protocol requirements
6. Unwilling to perform 3 to 4 finger stick blood glucose measurements daily
7. Use of Hydroxyurea medication
8. Poor vision (of primary caregiver) precluding the use of investigational technology

5.4 Participant withdrawal criteria

(a) when and how to withdraw participants from the investigational product/study treatment;
The participant may withdraw from the study at any time. They can do so by contacting the research staff.

(b) the type and timing of the data to be collected for withdrawn participant(s);
As this is an intention-to-treat, the data for withdrawn participants will be used for analysis

(c) whether and how participants are to be replaced;
Participants will not be replaced.

(d) the follow-up for participants withdrawn from the investigational product/study treatment.
The participants will go back on their standard therapy and will be followed up as their regular clinic visits.

6 Treatment of Participants

6.1 Description and justification for treatments, interventions or methods to be utilised

The Medtronic AHCL system comprises the Medtronic MiniMed™ 780G insulin pump containing the advanced closed loop algorithm, a next generation glucose sensor and transmitter. This system is the intervention provided to the participants for 3 months.

Rapid-acting Insulin is administered subcutaneously via the pump. The pump delivers insulin (microbolus) every 5 minutes and the amount is dependent on the sensor glucose levels. The system needs the entry of CHO amount by the user at meal times. This AHCL system has an advanced closed loop algorithm from the research studies (, RGS0000000886).

6.2 Permitted medications/treatments

For severe hypoglycaemia, intramuscular glucagon can be administered.

For ketosis > 0.6 mmol/l with blood glucose > 15mmol/l, insulin (rapid-acting) is administered with an insulin pen.

This is taught to every family at the time of diagnosis of T1D and review of their knowledge is established in subsequent clinic follow-ups.

6.3 Monitoring of participant compliance

The study is targeted at young children primarily supervised by parents/caregivers and hence a high degree of engagement with the study is expected.

Participants using the AHCL device will receive support from the research staff to help them familiarise themselves with the AHCL system. As this cohort is already on insulin pump therapy with most of the children on sensors, adaptation of this technology is not expected to be challenging.

Parents will also receive assistance to help troubleshoot sensor issues. They will be able to upload the pump at home, review reports and this will provide an opportunity to engage and encourage the use of the system.

7 Assessment of Efficacy

The efficacy of the device will be assessed through the Randomised Controlled Trial. 7.1 Primary outcomes

The primary outcome is the percentage of time spent in target glucose range (3.9-10 mmol/L) measured at 5-minutely intervals by a blinded CGM over 2 weeks starting at 13 - 15 weeks post randomization. Percentage of time spent in target glucose range will be calculated by dividing the number of sensor readings falling in the range 3.9-10 mmol/L by the total number of sensor readings and multiplying by 100. Participants will be considered to have missing data if they have fewer than 10 days with 70% valid sensor readings.

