Visit 4D: Review of AHCL (after 4 weeks from commencement of AHCL, 1 hour)

Face-to-face meeting to upload insulin pump, review CareLink reports and revise settings (CHO ratio and Insulin action time)

Participants will be issued with enough consumables for the study.

Research staff will review CGM data at 8 weeks' with participants encouraged to contact the team if support/assistance required.

VISIT 5 (11 weeks after randomisation for control arm only)

Visit 5A: Insertion of blinded CGM: This constitutes first of the two sensors, each sensor provides data for 7 days. Parents will be instructed to test their children for a minimum 3 to 4x/day using the study meter.

Visit 5B: Insertion of 2nd blinded CGM: Participants will return 7 days after sensor insertion to remove and download the first week of CGM data. The study meter will be uploaded. A new sensor will be inserted and a fresh transmitter attached.

A total of 2 weeks of blinded sensor is required with at least 10 days of data. In participants who do not meet this requirement, repeat sensors will be offered till a maximum of 4 attempts of data collection

Visit 5C: Insertion of 3rd blinded sensor (if applicable)

Visit 5D Insertion of 4th blinded sensor (if applicable)

VISIT 6 (1 week after last blinded sensor) **End of RCT Phase**

The following data will be collected:

1. Auxological
 - a. Height
 - b. Weight
 - c. BMI
2. Diabetes clinical
 - a. HbA1c
 - b. Total daily dose of insulin (mean of previous 7 days)
 - c. Pump upload (for intervention group)
 - d. Severe hypoglycaemia since Visit 5 for Control arm / Visit 4d for Intervention arm
 - e. Diabetic ketoacidosis since Visit 5 for Control arm / Visit 4d for Intervention arm
 - f. Hospital admissions since Visit 5 for Control arm / Visit 4d for Intervention arm
3. Psychology measures: Psychological scales will be administered to parents on an electronic platform.
 - a. Functional health status: Quality of life (QOL) WHO 5, EQ5D
 - b. Fear of hypoglycaemia: Hypoglycaemia fear survey Parent
 - c. Diabetes-related distress: Problem Areas in Diabetes PAID-Parent version
 - d. Anxiety: GAD-7
 - e. Sleep quality: Pittsburgh Sleep Quality Index
 - f. Technology acceptance and satisfaction: DTQ
4. 24-hour food recall interview (to capture dietary pattern)
5. Parents of participants will be offered a semi-structured interview at the end of the study to share the lived experiences with use of new technology.

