4.8 Trial Duration/Schedule

Feasibility Phase: For each participant, the study duration is 8 weeks.

RCT Phase: The trial is expected to take 24 months for recruitment, completion of study visits and data analysis. For each participant, the expected study duration is 3 months.

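### Section 7.1 starts the primary-outcome CGM at 13–15 weeks, but Visit 5 collects the controls' data from week 11, and no matching window is fixed for the AHCL arm

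*Protocol*

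**What the plan says.** Section 7.1 makes the primary outcome the percentage of sensor readings between 3.9 and 10 mmol/L, "measured at 5-minutely intervals by a blinded CGM over 2 weeks starting at 13 - 15 weeks post randomization". It gives one window and one sensor type, without distinguishing the arms.

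Section 4.2 schedules the collection differently:

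- "VISIT 5 (11 weeks after randomisation for control arm only"). A note to Figure 2 also limits the Visit 5 blinded CGM to controls.
- On the sensor fitted at Visit 5A: "This constitutes first of the two sensors, each sensor provides data for 7 days".
- On Visit 5B: "Participants will return 7 days after sensor insertion to remove and download the first week of CGM data". The second sensor is then fitted.
- On sufficiency: "A total of 2 weeks of blinded sensor is required with at least 10 days of data". Controls who fall short may have further sensors, up to four in all (Visits 5C and 5D).
- On the closing visit, for both arms: "VISIT 6 (1 week after last blinded sensor").

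Section 4.8 says of the RCT: "For each participant, the expected study duration is 3 months". Section 4.1 likewise places the primary endpoint at baseline and at three months.

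Section 7.1 has its own completeness rule: "Participants will be considered to have missing data if they have fewer than 10 days with 70% valid sensor readings".

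**The concern.** The sole confirmatory endpoint has two incompatible collection periods. A reader following section 7.1 looks for control data from week 13 at the earliest. A site following section 4.2 has usually removed the last control sensor by then.

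The AHCL arm has a further gap. It has no blinded sensor after baseline, so section 7.1 does not describe how its outcome is obtained, and Visit 6 is timed from a sensor it does not wear. Its study-system CGM runs continuously, so many 14-day stretches could serve as the outcome. The trial is open label (section 4.4). If the stretch is settled only once data are visible, the arms may be compared over different weeks, or the weeks may be chosen with knowledge of the results.

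A smaller mismatch concerns completeness. Repeat sensors depend on days of data, whereas missingness in section 7.1 depends on days that also reach 70% valid readings. On a literal reading, a control could satisfy the first rule, be offered no repeat sensor, and still be missing for the primary outcome.

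**Working it through.** **Inputs.** Section 7.1: window length 2 weeks, start between weeks 13 and 15. Section 4.2, Visit 5: first control sensor at week 11, 7 days per sensor, two sensors as standard, four at most. Sections 4.2 and 4.8: RCT duration 3 months.

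**Window as stated in section 7.1.** End = start + 2 weeks, so it runs from weeks 13–15 (earliest) to weeks 15–17 (latest). Three months is 365.25/12 × 3 / 7 = 13.0 weeks, so the window opens at or after the stated end of participation and closes about 2 to 4 weeks beyond it.

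**Control collection as scheduled.** With *k* consecutive sensors, data end at week 11 + *k*. Overlap with the earliest window is max(0, min(11 + *k*, 15) − 13). Overlap with the latest is max(0, min(11 + *k*, 17) − 15).

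| Sensors | Fitted at week | Data end | Overlap, weeks 13–15 | Overlap, weeks 15–17 |
|---|---|---|---|---|
| 2 (standard) | 11, 12 | 13 (day 91) | 0 weeks | 0 weeks |
| 3 | 11, 12, 13 | 14 (day 98) | 1 week | 0 weeks |
| 4 | 11, 12, 13, 14 | 15 (day 105) | 2 weeks | 0 weeks |

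Control CGM starts 13 − 11 = 2 to 15 − 11 = 4 weeks before the section 7.1 start. Read literally, the only controls with readings inside the window are those who needed repeat sensors.

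**Where 13–15 may come from.** 11 + 2 = 13 and 11 + 4 = 15, so the stated range is exactly when Visit 5 collection ends. Visit 6, if counted from insertion of the last sensor, also falls at weeks 13 to 15.

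**AHCL arm.** Section 4.2 gives it weekly uploads for 4 weeks after AHCL starts, a review visit at 4 weeks, a CGM review at 8 weeks and a pump upload at Visit 6. None of these fixes a 14-day outcome window or ties it to the controls' weeks.

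**Completeness rules.** At 5-minute intervals a full day has 24 × 60 / 5 = 288 readings, and 70% is 201.6, so a valid day needs 202. As an illustration, take a control with data on 10 days, 3 of them below 202 readings. The Visit 5 rule read literally is met (10 days), but the section 7.1 rule is not (7 days).

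**The case against.** The strongest reply is that this is one wrong word. If *starting* is read as *ending*, the control dates reconcile exactly. Other text fits that reading: section 4.1 puts the endpoint at three months, section 7.2 reports the effect at the end of the study, and section 9.1 uses Visit 6 data. Figure 2 is not available to check. The slip is plausible, but it remains an inference. It would repair the control dates only: the AHCL arm would still have no blinded sensor and no anchor for Visit 6. An SAP may name an extraction window, but it cannot make the protocol's two statements agree.

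Several stronger readings are tempting and do not hold:

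- A reader might infer that control data end before the window. On two sensors they end as it opens; permitted repeat sensors carry them into it.
- A reader might infer that every control with two working sensors is missing for the primary outcome. The section 7.1 missing-data rule counts days and valid readings, not calendar weeks, so 14 good days from week 11 are not missing under it.
- A reader might infer that the protocol assigns the arms different weeks. Section 7.1 gives one window; the fault is that the schedule does not deliver it.
- A reader might try to quantify unequal AHCL exposure. Visits 3 and 4A may be combined, as may 4A and 4B. Visit 4C follows a few days of CGM, and sensor-naive children have 7 to 10 days of familiarisation. No upper limit is set, so the AHCL start time would have to be assumed.

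On completeness, the Visit 5 wording may be shorthand for the section 7.1 rule. That is possible, and one sentence would settle it. That losses would fall mainly on controls is conjecture, and section 9.7 already plans both multiple imputation and complete-case analyses.

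**Conclusion.** The contradiction stands. As written, section 7.1 cannot be followed: the scheduled control data have no overlap with its window on the standard two-sensor schedule, and at most two weeks with all four sensors. The required blinded CGM does not exist at end of study in the AHCL arm, whose 14 days are not anchored to the controls' weeks. This holds whether or not *starting* is a slip.

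The arithmetic assumes Visit 5A takes place at week 11 and sensors are worn consecutively for 7 days each. The documents do not show that time in range differs between weeks 11–13 and 13–15, so no size or direction of bias can be given. The sample size is unaffected by the timing. The risk is of unmatched or analyst-chosen windows for the primary endpoint in an unblinded trial, and the passages should be reconciled before the outcome is extracted.

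**What to change.** 1. Rewrite section 7.1 with one window for both arms that matches Visit 5: the 14 days starting 11 weeks after randomisation, extended only by permitted repeat sensors.
2. State the source in each arm: the blinded sensor for controls, and study-system CGM from pump upload for AHCL. Confirm an upload covering those weeks, since weekly uploads are specified only for the first 4 weeks of AHCL use.
3. Anchor Visit 6 to weeks since randomisation in both arms.
4. Use the section 7.1 completeness rule as the repeat-sensor trigger, assessed when the second sensor is removed (Visits 2B and 5C). At Visits 2A and 5B only 7 days exist, so a 10-day rule cannot yet be judged.

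Moving Visit 5A to week 13 is a poorer alternative. Control collection would then run over weeks 13–15, or to week 17 with four sensors, beyond the 3-month participation. By the protocol's own dates (start August 2021, version 9 of November 2022) the trial is under way, so control windows would also be split between earlier and later participants.

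The cost is mainly wording, an upload check in the AHCL arm, and a few more repeat sensors within the four already allowed.
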